This data analysis plan (DAP) is intended to be a comprehensive and detailed description of the strategy, rationale, and statistical techniques that will be used to address the clinical safety, tolerability, and immunogenicity of the quadrivalent HPV (Types 6, 11, 16, 18) L1 VLP vaccine and the efficacy of the vaccine in the prevention of HPV 16 and 18-related CIN 2/3 or worse in 16- to 23-year-old women. Protocol 015 and Amendment 015-01 are covered by this DAP. The protocol is entitled, “A Randomized, Worldwide, Placebo-Controlled, Double-Blind Study to Investigate the Safety, Immunogenicity, and Efficacy on the Incidence of HPV 16/18-Related CIN 2/3 or Worse of the Quadrivalent HPV (Types 6, 11, 16, 18) L1 Virus-Like Particle (VLP) Vaccine in 16- to 23-Year-Old Women—The FUTURE II Study (Females United to Unilaterally Reduce Endo/Ectocervical Disease).”

B. Description of the Study and Objectives/Hypotheses

1. Study Design

Protocol 015 is a prospective randomized, double-blind, placebo-controlled, parallel, multicenter study operating under in-house blinding procedures. Embedded within Protocol 015 is a consistency lot substudy. Approximately 11,500 subjects will be randomized in a 1:1 ratio to receive either 3 injections of quadrivalent HPV (Type 6, 11, 16, 18) L1 VLP vaccine or 3 injections of placebo. Within the quadrivalent HPV vaccine group, subjects will be further randomized to receive 3 different lots of the vaccine in a 1:1:1 ratio. The actual lots received will differ between subjects enrolled in the consistency lot substudy and the remaining subjects in Protocol 015. Each dose of quadrivalent vaccine will contain 20 µg HPV 6 L1 VLP, 40 µg HPV 11 L1 VLP, 40 µg HPV 16 L1 VLP, and 20 µg HPV 18 L1 VLP. Vaccine or placebo is administered at 0, 2, and 6 months. Approximately 1 month following the third vaccination visit (Month 7), 6 months following the third vaccination visit (Month 12) and every year thereafter until Month 48, subjects will return to the study center for collection of specimens, gynecologic examinations, and Pap tests.

While most subjects in Protocol 015 will be followed only for the occurrence of serious adverse experiences (SAEs) following vaccination, the subjects who enroll in the United States (~1150 of the subjects [10%]) will participate in a nonserious adverse experience (NSAE) substudy. These subjects will undergo a full assessment of nonserious adverse

B. Description of the Study and Objectives/Hypotheses (Cont.)

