The primary endpoint for safety is the incidence of vaccine-related serious adverse experiences. Point estimates of the incidence of serious adverse experiences and vaccine-related serious adverse experiences and the corresponding 95% confidence intervals will be provided for each treatment group for all subjects enrolled in the study.

A. Special Safety Analysis (Cont.)

Severe injection site reactions are also of special interest. Therefore, for all subjects enrolled in the NSAE substudy and in the United Kingdom, point estimates of the incidences of severe injection site reactions will be provided for each treatment group along with the corresponding 95% confidence intervals.

For all subjects enrolled, pregnancies that occur during the study and their outcomes will be tabulated by treatment group and overall. Pregnancies that were detected anytime between Day 1 and 1 month following the completion of the vaccination regimen (Month 7) will be summarized separately from those detected following Month 7. In addition, the outcomes of all breast-feeding experiences in subjects who were breast-feeding during the vaccination regimen will be tabulated by treatment group and overall.

B. Adverse Experiences

To reduce the number of statistical tests performed for adverse experiences and the accompanying multiplicity issues associated with them, the following approach will be used for the analyses of adverse experiences. These analyses will be performed using the subset of subjects participating in the NSAE substudy only.

To provide an overall assessment of safety, measures such as the incidence of: (1) any adverse experience, (2) any injection-site adverse experience, (3) any systemic adverse experience, and (4) any vaccine-related adverse experience that occurred throughout the study will be summarized.

To address specific adverse experiences, the incidences of injection-site adverse experiences Days 1 to 5 and specific systemic adverse experiences within 14 days postvaccination occurring in at least 1% of the subjects will be tabulated across injections. Risk differences will be estimated, and the associated 95% two-sided confidence intervals will be provided. The method of Miettinen and Nurminen [1] will be used for all comparisons.

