The final analysis of Protocol 015 will be performed when at least 29 cases of the primary endpoint have been observed regardless of the outcome of the interim analysis. This will allow for an assessment of longer-term vaccine efficacy and will allow a sufficient number of cases of CIN 2/3 or worse due to any cause to accrue for a secondary analysis of this endpoint using the combined data sets from Protocols 005, 007, 013, and 015 (this analysis is outlined in the combined analysis DAP). A multiplicity adjustment will be made to account for the 2 separate analyses of Protocol 015. A two-sided alpha of 0.0204 will be spent at the interim analysis, and a two-sided alpha of 0.0411 will be spent at the final analysis.

B. Safety

In order to ensure that no alarming, unusual, or unexpected safety problems are occurring with the vaccine, safety will be monitored during the study by the DSMB who will determine if any actions should be taken based on the data. Periodically during the study (approximately every 6 months during the vaccination period and approximately every year thereafter), all available safety data from the study will be summarized by the designated unblinded Merck statistician and sent to the DSMB. Summaries will also be provided in the event that there is a specific safety concern during the study.

In general, adverse experiences will be summarized descriptively as frequencies and percentages by treatment group and type of adverse experience (this will be done by vaccination visit and across all vaccination visits), and temperatures will be summarized. The DSMB manual specifies the details of the operating procedure for this process.

In particular, the DSMB will monitor the following parameters during the course of Protocol 015:

B. Safety (Cont.)

- the incidence and characteristics of serious adverse experiences;
- the incidence and characteristics of nonserious adverse experiences – a general summary will be provided as well as summaries of specific injection-site and systemic adverse experiences;
- pregnancies and their outcomes;
- the incidence of breast-feeding during the vaccination period and the associated outcomes; and
- new medical conditions that arise during the study.

Serious adverse experiences will be reported to the DSMB at the same time Merck reports them to the FDA.

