Each of the subjects in each study will receive 3 doses of quadrivalent HPV (Types 6, 11, 16, 18) L1 VLP vaccine or placebo. The vaccine or placebo will be administered at 0, 2, and 6 months. For the efficacy analyses, there will be no restrictions placed on the timing of the 3 vaccination visits as long as they occur within 1 year, or any of the follow-up visits with the exception of the Month 7 visit. The postvaccination clinical samples collected at the Month 7 visit will only be considered as valid for establishing the PCR status of a subject if they are obtained 14 to 72 days following the Month 6 vaccination.

For the per-protocol immunogenicity analyses, acceptable timing for the Month 2 vaccination visit will be 36 to 84 days (60 days \pm 24 days), and acceptable timing for the Month 6 vaccination visit will be 148 to 218 days (183 days \pm 35 days). The postvaccination clinical samples collected at Month 7 will be considered for the immunogenicity analyses if they are obtained 14 to 49 days (2 to 7 weeks) following the Month 6 vaccination. The acceptable day range for vaccination are slightly wider than the day ranges specified in the protocol to allow for differences in counting when defining a "month" (calendar month versus 30 days). The day range for the Month 7 visit is slightly wider than that specified in the protocol to ensure that all HPV protocols use consistent day ranges in their analyses. (The Phase I protocols specified slightly different ranges for the Month 7 visit [2 to 6 weeks postdose 3] than the Phase II/III studies [3 to 7 weeks postvaccination]).

The allowable day range for the Month 7 visit is narrower for the immunogenicity analyses than for the efficacy analyses because in the immunogenicity analyses, it is important to try to measure a Postdose 3 immune response that is as close to the peak response as possible. The goal of the Month 7 visit for the efficacy analyses is to provide an assessment of the subjects' "1 month Postdose 3" HPV status and mark the beginning of the follow-up period.

For the immunogenicity analysis of the persistence of antibody titers, only Month 24 serum samples collected 639 to 821 days (730 days \pm 91 days)

A. Definition of Time Points (Cont.)

Postdose 1 and Month 48 serum samples collected 1369 to 1551 days (1460 days \pm 91 days) Postdose 1 will be considered. These day ranges will be imposed on both the per-protocol and all type-specific HPV naïve subjects with serology data populations.

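### Pregnancies are split only by date of detection, so a signal confined to conceptions near a dose, dose 3 above all, would be hard to see

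*SAP*

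**What the plan says.** Section V.A first gives an undivided table: for everyone enrolled, "pregnancies that occur during the study and their outcomes will be tabulated by treatment group and overall". It then makes one division by time: "Pregnancies that were detected anytime between Day 1 and 1 month following the completion of the vaccination regimen (Month 7) will be summarized separately". The other group consists of pregnancies found after that point. The deciding variable is detection. The SAP has no rule based on estimated conception date, last menstrual period or interval from a dose, and makes no allowance for the time between conception and detection.

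Other sections bear on this:

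- Section I.B.1 (Study Design) gives the schedule: "Vaccine or placebo is administered at 0, 2, and 6 months". Visits follow at Months 7 and 12 and then "every year thereafter until Month 48".
- Section VIII.A (Definition of Time Points) accepts Month 7 samples for PCR status "if they are obtained 14 to 72 days following the Month 6 vaccination". This window governs samples, not pregnancies. For efficacy, the same section leaves the vaccination visits free as long as all three fall within 1 year.
- Section VIII.E.2.c foresees women who become pregnant before Month 6, continue the pregnancy and still receive all three injections within 1 year.
- Section VI.B lists "pregnancies and their outcomes" among the items that the DSMB monitors, without applying the Month 7 division to them.

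**The concern.** A reader would naturally use a cut one month after the last dose to look at pregnancies close to vaccination apart from later ones. Date of detection serves that use poorly. A pregnancy is always found after it begins, so a cut placed only about a month after dose 3 sends many pregnancies conceived in that month to the later table, which runs to Month 48. The early table also mixes conceptions near a dose with those in the four-month gap between doses 2 and 3.

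The boundary is loosely defined as well. It is one month after completing the regimen, with Month 7 given as its equivalent. A woman who stops after one or two injections has no completion date. A woman whose third injection is delayed has a completion date well after the nominal month.

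At stake is whether the planned tables could show an effect on outcome that is limited to conceptions near an injection.

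**Working it through.** The SAP gives no pregnancy rate, detection lag or effect size, so there is no planned figure to reproduce. The calculation below is an illustration.

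**Inputs from the SAP.** Doses are at Months 0, 2 and 6, the cut is at Month 7 and follow-up ends at Month 48. The later table therefore covers 48 − 7 = 41 months.

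**Assumptions, not in the SAP.**
- Conceptions occur at a constant rate, equal in both arms.
- A month is 30 days.
- Detection comes L = 14, 21, 28 or 42 days after conception.
- Near-dose means conceived within 30 days after a dose.

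**Step 1: conceptions in the 30 days after dose 3 that land in the later table.** With the cut V days after dose 3, a conception on day c is classed as later if c + L > V. The share is (30 − (V − L))/30, limited to the range 0 to 1.

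| Cut V | L = 14 | L = 21 | L = 28 | L = 42 |
|---|---|---|---|---|
| day 14 | 100% | 100% | 100% | 100% |
| day 30 | 47% | 70% | 93% | 100% |
| day 49 | 0% | 7% | 30% | 77% |
| day 72 | 0% | 0% | 0% | 0% |

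For example, V = 30 and L = 14 gives 14/30 = 47%. Days 14 and 72 are the limits of the efficacy sample window in section VIII.A, and day 49 is the upper limit for immunogenicity samples. They matter only if the actual Month 7 visit is the cut, which V.A does not say.

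**Step 2: share of all near-dose conceptions that move (day-30 cut).** Three doses give 3 months of near-dose conceptions, and only the month after dose 3 is affected. The amount moved, m, is L/30 months, at most 1. The share is m/3: 0.467/3 = 16%, 0.70/3 = 23%, 0.933/3 = 31%, 1/3 = 33%.

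**Step 3: their weight in the later table.** m/41: 0.467/41 = 1.1%, 0.70/41 = 1.7%, 0.933/41 = 2.3%, 1/41 = 2.4%.

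**Step 4: what each table would show.** Suppose, for illustration only, that vaccine doubles the risk of an adverse outcome in near-dose conceptions and has no effect otherwise. The vaccine-to-placebo ratio in a table is then 1 + (2 − 1) × (near-dose fraction).

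- Early table, cut at Month 7 by conception date: 3/7 = 0.429, ratio 1.43.
- Early table, cut by detection date: (3 − m)/(7 − L/30). For L = 14, 2.533/6.533 = 0.388; for 21, 2.3/6.3 = 0.365; for 28, 2.067/6.067 = 0.341; for 42, 2.0/5.6 = 0.357. The ratios run from 1.34 to 1.39.
- Later table, cut by detection date: 1 + m/41, or 1.01 to 1.02.
- A separate near-dose class, correctly dated: fraction 1, ratio 2.

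Detection dating lowers the early ratio from 1.43 to 1.34–1.39. Most of the fall from 2 comes from the width of the Day 1 to Month 7 window.

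**Step 5: the boundary.** Section VII.A.1 assumes attrition of no more than 15% through Month 7. That is at most 0.15 × 11,500 = 1,725 women, not all of whom would lack dose 3. If dose 3 comes near the 1-year limit, one month after completion is about Month 13, not Month 7. V.A does not say which date governs.

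**The case against.** The strongest reply is that V.A states no purpose for the split. Section I.B.2 makes Month 7 the primary time point for safety, and section VII.C describes a cleaned database copy through Month 7. Detected by Month 7 may be simply a reporting cut, not a failed classification of exposure. That is a fair reading. It leaves the SAP with no table by proximity to a dose, so the gap stands.

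Other parts of the reply also stand. No pregnancy is dropped, both arms follow the same rule, and no test or decision criterion is attached. The misclassified share rests on an assumed lag and an assumed day-30 cut, and it falls to zero across the lags considered if the cut is a visit at day 72. The loss in the early table from detection dating alone is modest. For women who do not complete the regimen, Month 7 can be read as a nominal date, so the cut is unclear for them rather than impossible to apply.

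Three stronger conclusions are tempting but unsupported. A reader might infer that the vaccine-placebo comparison of pregnancy outcomes is biased; it is not, because the undivided table by treatment group remains. A reader might treat the later period as the comparator; the tables are by treatment group, so the comparator is placebo within each period. A reader might also infer that DSMB monitoring is weakened; section VI.B does not apply this split, and it leaves operating detail to a DSMB manual that is not shown.

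**Conclusion.** The point holds as a limited one. The only planned division of pregnancies by time uses detection and so does not measure closeness to vaccination. With a day-30 cut and a lag of 14 to 42 days, 47% to 100% of conceptions in the month after dose 3 go to the later table. That is 16% to 33% of all conceptions within 30 days after any dose, and they form about 1% to 2.4% of the later table. Under the illustrative risk ratio of 2, the later table would show 1.01 to 1.02, so an effect confined to dose 3 conceptions would be practically invisible there.

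These sizes depend on the assumed lag, the constant conception rate and the position of the cut. The direction does not: with any positive lag and a cut 30 days after dose 3, some of these conceptions are classed as later. The consequence is reduced ability to see a signal near a dose. The change is cheap and worth making.

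**What to change.** Keep the planned tables. Add to V.A a tabulation of pregnancy outcomes by treatment group, classified by estimated date of conception relative to the nearest injection actually received: for example within 30 days of any injection, more than 30 days from any injection, before the first injection, and unknown. State whether the window covers days before as well as after an injection, and which class takes precedence where two could apply, so that each pregnancy is counted once. The 30 days is an example for the sponsor to settle before unblinding.

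The new table needs neither a completion date nor a Month 7 visit, so it covers women who stop early or finish late. For the retained detection-date table, add a clause saying whether nominal Month 7, the actual visit or one month after the last injection received sets the cut.

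The cost is one derived date, one table and a short paragraph. It assumes that last menstrual period or gestational age is recorded, which the SAP alone does not show. Some conception dates will be imprecise or missing, hence the unknown class.

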While most subjects in Protocol 015 will be followed only for the occurrence of serious adverse experiences (SAEs) following vaccination, the subjects who enroll in the United States (~1150 of the subjects [10%]) will participate in a nonserious adverse experience (NSAE) substudy. These subjects will undergo a full assessment of nonserious adverse experiences that occur within 14 days following each vaccination visit in addition to the follow-up for serious adverse experiences. Subjects enrolled in the United Kingdom will also undergo active follow-up for nonserious adverse experiences, as this is a regulatory requirement in the United Kingdom. Subjects at all other study sites may report nonserious AEs spontaneously, but there will be no solicitation for such events at these study sites.

Approximately 3000 of the subjects in Protocol 015 will be enrolled into the consistency lot substudy. The subjects in the consistency lot substudy will be randomized in a 1:1:1:3 ratio to receive Consistency Lot 1 of the quadrivalent HPV (Types 6, 11, 16, 18) L1 VLP vaccine, Consistency Lot 2 of the quadrivalent HPV (Types 6, 11, 16, 18) L1 VLP vaccine, Consistency Lot 3 of the quadrivalent HPV (Types 6, 11, 16, 18) L1 VLP vaccine, or placebo. Therefore, among the 3000 subjects enrolled in the substudy, 1500 will be randomized to receive the quadrivalent HPV (Types 6, 11, 16, 18) L1 VLP vaccine, and 1500 will be randomized to receive placebo. The placebo subjects will be enrolled in the consistency lot substudy only to maintain blinding and to maintain the 1:1 ratio of subjects in the vaccine and placebo treatment groups for the larger efficacy study. These subjects will not be used to address the immunogenicity objectives of the substudy. The 1500 subjects randomized to receive the quadrivalent HPV (Types 6, 11, 16, 18) L1 VLP vaccine will be randomized in a 1:1:1 ratio to receive 1 of 3 consistency lots of quadrivalent HPV (Types 6, 11, 16, 18) L1 VLP vaccine.

The efficacy study employs a fixed-number-of-events design. An interim analysis addressing the primary efficacy hypothesis of the study is planned to be conducted at the time that at least 19 cases of CIN 2/3 or invasive cervical cancer related to HPV 16 or 18 have been observed. The final efficacy analysis will be conducted when at least 29 cases have been observed.

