experiences that occur within 14 days following each vaccination visit in addition to the follow-up for serious adverse experiences. In addition, due to regulatory requirements in the United Kingdom, all subjects enrolled in the United Kingdom will be solicited for serious and nonserious adverse experiences that were observed during the 14 days following each vaccination as well. The method for collecting nonserious adverse experience data will be different in the NSAE substudy and in the United Kingdom. In the NSAE substudy, each subject will record any nonserious adverse experiences that she observes during the 14-day follow-up period on a vaccination report card that is sent home with her at the vaccination visit. She will return the report card to the study site at the next scheduled visit, and the data will be entered from the report card into the study database. (The data will have been captured in writing by the subject during the appropriate period, however.) In the United Kingdom, subjects will not receive a vaccination report card. However, at each visit after a vaccination visit, each subject will be asked by study site personnel to recall any nonserious adverse experiences that occurred during the 14-day period following the prior vaccination. Subjects enrolled in study sites outside of the United States and the United Kingdom may report nonserious adverse experiences spontaneously, but solicitation for such events will not be conducted at these study sites.

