Statistical testing will be conducted for the specific adverse experiences for which subjects were prompted on the vaccination report card. Therefore, the proportions of subjects who experience redness, swelling, and pain/tenderness at the injection site and the proportions of subjects with elevated temperatures ($\geq 100^{\circ}\text{F}$, oral equivalent) will be formally analyzed. In addition to the count and the percentage, the risk difference, the associated 95% confidence interval, and the two-sided p-value testing for a difference in incidence rates will be presented.

B. Adverse Experiences (Cont.)

Separate summaries will be performed for subjects who are: (1) seronegative at Day 1 and PCR-negative Day 1 through Month 7 to all 4 vaccine components, and (2) seropositive at Day 1 or PCR-positive at any time between Day 1 and Month 7 to at least 1 vaccine component. Tabulations of adverse experience data by injection will also be provided.

The distribution of adverse experiences across severity/intensity ratings will also be provided for each treatment group across all injections. Each episode of each reported adverse experience will be counted separately for this summary. The summary will be provided for any adverse experiences, any systemic adverse experiences, and any injection-site adverse experiences. For the measured adverse experiences of redness and swelling, 0 to 1 inch will be categorized as mild, >1 inch but ≤ 2 inches will be categorized as moderate and >2 inches will be categorized as severe. In addition, the distribution of injection-site adverse experiences will be summarized separately by adverse experience for the “prompted” adverse experiences of pain/tenderness/soreness, redness, and swelling.

To complement the analyses above, the number of subjects reporting an adverse experience within each severity/intensity category will be summarized across all adverse experiences reported. Each subject will be counted only once in these summaries. The worst severity/intensity rating will be utilized for each subject. These summaries will be performed for any adverse experiences, any injection-site adverse experiences, and any systemic adverse experiences. The summaries will be provided for each treatment group across all injections.

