For specific injection-site adverse experiences Day 1 to 5 postvaccination and specific systemic adverse experiences Day 1 to 14 postvaccination with an incidence of $\geq 1\%$ in either treatment group, the distribution of maximum severity per subject will also be tabulated by treatment group in Section II.11 of the clinical study report (CSR). For the measured injection-site adverse experiences that are prompted for on the VRC Days 1 to 5 postvaccination, erythema (redness) and swelling, the distribution of maximum reported size will also be tabulated by treatment group.

VI. INTERIM ANALYSES/DATA AND SAFETY MONITORING BOARDS

A. Efficacy

An interim efficacy analysis of Protocol 015 is planned to be conducted at the time that at least 19 cases of the primary endpoint have been observed. The interim analysis will involve a test of the primary hypothesis in the per-protocol and the first 2 MITT populations. An estimate of the incidence rate of all CIN 2/3 will also be provided. The critical database fields for identifying protocol violators, identifying cases, and conducting the primary analysis will be identified, and all critical data that are in-house will be screened prior to the interim analysis. A separate document outlining the critical data fields and detailed screening plan will be written.

The interim analysis of Protocol 015 will be performed in conjunction with an interim analysis of the combined data from Protocols 005, 007, 013, and 015, and, therefore, will only be conducted when at least 19 cases of CIN 2/3 or cervical cancer related to HPV 16 or 18 have been observed in Protocol 015 *and* at least 33 cases have been observed across all 4 studies.

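### Local reactions are recorded for 14 days, but the by-type incidence and maximum-severity tables stop at Day 5, so an unprompted type starting on Days 6 to 14 has no planned by-type comparison

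*SAP*

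**What the plan says.** **Collection.** The SAP Executive Summary (Study Design) says that subjects enrolled in the United States undergo a "full assessment of nonserious adverse experiences that occur within 14 days following each vaccination visit". Section I.B.1 gives the mechanism: "each subject will record any nonserious adverse experiences that she observes during the 14-day follow-up period on a vaccination report card". Neither place sets a shorter recording period for local reactions.

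**By-type tables.** Section V.B, which applies to the NSAE substudy only, plans to tabulate across injections "the incidences of injection-site adverse experiences Days 1 to 5 and specific systemic adverse experiences within 14 days postvaccination", limited to events in at least 1% of subjects, with risk differences and 95% confidence intervals. Later in V.B the maximum-severity table opens in the same way: "For specific injection-site adverse experiences Day 1 to 5 postvaccination and specific systemic adverse experiences Day 1 to 14 postvaccination", with a threshold of 1% in either group.

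**Prompted reactions.** V.B also plans formal testing of "the proportions of subjects who experience redness, swelling, and pain/tenderness at the injection site" (and of elevated temperature), with count, percentage, risk difference, confidence interval and p-value. It adds that "the distribution of injection-site adverse experiences will be summarized separately by adverse experience for the" three prompted reactions. Neither statement carries a day window. The only mention of when the card prompts is in the size tabulation for redness and swelling, which are called "measured injection-site adverse experiences that are prompted for on the VRC Days 1 to 5 postvaccination".

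**The concern.** A table window shorter than the recording window leaves collected data out of the analysis, and here it does so for one class of event only. Unprompted systemic events from the same card are tabulated for the full 14 days, while unprompted local events are cut at Day 5. Delayed local reactions to an injected vaccine would fall in the part left out.

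What is at stake is the description of local tolerability against placebo. No hypothesis, success criterion or primary safety estimate depends on these tables. However, the SAP names severe injection-site events among its primary safety variables (Executive Summary, Endpoints), so a reader of the study report will look for a full account of local reactions.

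The missing window for the prompted-reaction analyses is a separate, smaller problem. Two programmers could reasonably choose different windows and produce different counts and p-values for the only local reactions that are formally tested.

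**Working it through.** The SAP attaches no sample size, power or alpha to this choice, so the check compares windows.

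**Days outside the by-type tables.** Recording runs 14 days per dose (Executive Summary; I.B.1), and the by-type tables cover Days 1 to 5 (V.B). 14 − 5 = 9 days per dose, namely Days 6 to 14. Over three doses, 3 × 9 = 27 of 3 × 14 = 42 recorded days. These are calendar days, not events.

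**Where a local reaction starting on Days 6 to 14 is counted.**

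| Planned summary (SAP section) | Window stated | By type? |
|---|---|---|
| Incidence with risk difference (V.B) | Days 1 to 5 | Yes |
| Maximum severity per subject (V.B) | Days 1 to 5 | Yes |
| Maximum size, redness and swelling (V.B) | Days 1 to 5 | Yes, these two only |
| Formal comparison of prompted reactions (V.B) | None | Yes, prompted types only |
| Episode severity for prompted reactions (V.B) | None | Yes, prompted types only |
| Any injection-site event; its episode and worst-severity distributions (V.B) | No Day 5 limit | No |
| Severe injection-site reactions with 95% CI, NSAE substudy plus UK (V.A) | No Day 5 limit | No |
| Tabulations by injection (V.B) | None | Not specified |
| Summaries of specific injection-site events for the data and safety monitoring board (VI.B) | None | Yes, but for monitoring |

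**An unprompted type.** Of the rows above that are by type and belong to the study report, the first two stop at Day 5 and the other three cover prompted reactions only. The tabulations by injection specify neither type nor window, so they cannot be relied on. No row therefore gives a by-type incidence, risk difference or severity for an unprompted local reaction starting on Days 6 to 14. The pooled rows do count it, but a woman who already had an early local reaction is already in the any-event total, so her later reaction of another type need not change that incidence.

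**A prompted type.** The formal comparison and the episode-severity distribution would include a late redness, swelling or pain event if their window is 14 days, and would exclude it if it is 5. V.B supports either reading. Its paragraph on testing has no limit, but its size tabulation refers to prompting on Days 1 to 5 for redness and swelling. It says nothing on the prompting window for pain/tenderness.

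**Number of events.** The SAP gives no rate of local reactions starting after Day 5, so none can be derived.

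**The case against.** The strongest defence is that the Day 5 cut matches how the card solicits: redness and swelling are prompted on Days 1 to 5. A single Days 1 to 14 rate could mix prompted and unprompted reporting, so a table aligned with prompting is defensible. This stands as a reason to keep the Days 1 to 5 rows and to footnote any later ones. It does not explain applying the cut to injection-site types that are not prompted, when unprompted systemic events on the same card get 14 days. V.B's stated wish to limit the number of tests does not explain it either, because the by-type table presents risk differences and intervals, with testing confined to prompted events.

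A second defence is that late local reactions are not lost. This also stands. They enter the any-injection-site and severe-reaction summaries, and the monitoring board receives summaries of specific injection-site events by treatment group.

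A reader might therefore go too far by inferring that every delayed local reaction lacks any incidence, risk difference or severity by type. The SAP does not support this for redness, swelling and pain/tenderness, where a by-type comparison and a severity distribution are planned without a stated Day 5 limit. A reader might also infer that late reactions are never compared with placebo by type, which overlooks the board's summaries. Finally, a reader might infer a sizeable hidden safety signal. The SAP gives no late-reaction rate on which to base one, and any assumed split between arms would be invented.

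**Conclusion.** The point holds for unprompted local reaction types. For these, the study report has no planned by-type incidence, risk difference or severity on Days 6 to 14, although the data are on the card. For redness, swelling and pain/tenderness the defect is an unstated window, not an omission.

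The extent is 9 of 14 recorded days per dose; the number of events is unknown. The conclusion assumes that the report card takes local events over the full 14 days, as the SAP's wording indicates, and that the tabulations by injection add no by-type detail beyond what is written. It is a modest descriptive gap that costs little to close.

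**What to change.** In SAP section V.B:

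- Keep the Days 1 to 5 injection-site rows in the incidence/risk-difference table and in the maximum-severity table.
- Add by-type injection-site rows for Days 6 to 14 (or Days 1 to 14) to both tables, with counts, risk differences, 95% confidence intervals and maximum severity. Keep these descriptive, with no added tests, and apply the 1% threshold to the added window so that a type appearing only late can have a row.
- State the day window for the formal comparison of redness, swelling and pain/tenderness and for their severity distribution.
- Footnote that Days 6 to 14 may be unprompted for some reactions.

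The cost is SAP wording and a few more table rows. The only drawback is that prompted and unprompted reporting may not be directly comparable, which the separate rows and the footnote make visible.
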